### **Participants**

Patients >= 18 years old undergoing clinic-based "minor" eyelid procedures in clinic with at least one lesion.

Inclusion criteria:

- 1. Age >=18 years old
- 2. Any eyelid lesion presenting to clinic setting Exclusion criteria
- 1. Any other topical, PO or IV sedating medications given alongside procedure
- 2. Allergy to lidocaine or epinephrine

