#### **Outcome Measures**

Primary

- 1. Pain during injection (1-10)
- 2. Pain during procedure (1-10)

Secondary

- 1. Bleeding requiring >5 minutes of firm pressure or cautery
- 2. Need for additional anesthesia

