# **Study Protocol**

Prior to clinic day, patient list will be reviewed to identify potentially eligible patients. On the procedure day, eligible patients will be approached for participation following initial evaluation by attending physician. If patient amenable, patient will be consented for study. Photograph will be taken of the lesion directly in electronic medical record, and lesion circled using annotate function. Each lesion will be randomized separately using iPhone-based randomization application to either bacteriostatic saline or lidocaine with epinephrine. Fellow will be unblinded, attending physician blinded. Medication will be drawn up by fellow and handed to attending physician who will inject the medication. Immediately following injection, patient will be asked pain level on 0 to 10 scale, which was noted. Five minutes will be allowed to pass and then procedure will be commenced. If patient has more pain than acceptable to them, additional study agent will be injected and procedure re-started. If continued presence of pain, one more additional trial of the study agent will be allowed. If patient continues to have pain, medication will be defaulted to standard of care (lidocaine with epinephrine). Alternatively, if patient requests standard of care at any point, medication will be switched to this. Immediately following procedure, patient will be asked pain level on 0 to 10 scale, which was noted. Number of reinjections or need to default to standard of care will be noted. Bleeding level (Mild, moderate, or severe) will be noted. Mild is defined as not needing pressure to stop. Moderate is defined as needing five minutes or pressure to stop. Severe is defined as needing cautery or a pressure patch. Immediately following injection, patient will be asked pain level on 0 to 10 scale.

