# **Statistical Plan**

Pain of injection and pain of procedure are recorded on a categorical scale and compared using Student T-Tests. Percent of lesions requiring reinjection and percentage of lesions with "severe" bleeding were compared using Chi-square tests. To see if lesions size had any effect on these metrics, the lesions will be divided into < 1 mm, 1-5 mm, and > 5 mm, and analysis will be repeated on these groups.

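### Both primary pain comparisons are unadjusted t-tests; lesion size, which the plan needs for every lesion, is used only for band-by-band repeats and adds no precision to the overall arm comparison

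*Combined protocol and SAP*

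**What the plan says.** The Statistical Plan gives the whole primary analysis in one sentence: "Pain of injection and pain of procedure are recorded on a categorical scale and compared using Student T-Tests". It names no covariate, stratification factor or model.

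Lesion size appears in the last sentence of the same section. Its purpose is "To see if lesions size had any effect on these metrics", where the metrics are the two pain scores, reinjection and severe bleeding. The method is that "the lesions will be divided into < 1 mm, 1-5 mm, and > 5 mm, and analysis will be repeated on these groups".

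Three statements elsewhere bear on this:

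- **Randomisation (Study Protocol):** "Each lesion will be randomized separately using iPhone-based randomization application". No stratification by size is mentioned.
- **Lesion record (Study Protocol):** before the randomisation step, "Photograph will be taken of the lesion directly in electronic medical record, and lesion circled using annotate function". No step for measuring size is described.
- **Participants:** patients enter "with at least one lesion", so one patient may contribute several.

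The documents give no sample size, SD, target difference, alpha, power or correlation between size and pain.

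**The concern.** The plan regards lesion size as a possible influence on pain and must have it for every lesion to assign the bands, yet the main result makes no use of it. If size does predict pain, the variation between lesions that it causes stays in the error term of both t-tests. A chance difference in size between the arms then also adds noise to the estimated difference.

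Repeating the tests within bands does not recover this. Each repeat uses only part of the data and yields its own arm difference, and the overall comparison is left as it was. What is at stake is the width of the confidence interval for each primary comparison. Whether the treatment effect changes with size is a separate question.

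**Working it through.** **No figure to reproduce.** The plan states no sample size or power. The calculation therefore starts from an assumed comparison with 80% power unadjusted, at two-sided alpha 0.05. R² is the assumed share of pain variance explained by size. Lesions are treated as independent.

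**Step 1: gain, ignoring the cost of estimating the covariate's slope.** Adjustment multiplies the residual variance by 1 − R². The equivalent gain in lesions is 1/(1 − R²) − 1. Power becomes Φ((1.96 + 0.8416)/√(1 − R²) − 1.96).

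| Assumed R² | Equivalent extra lesions | Argument of Φ | Power |
|---|---|---|---|
| 0 | 0% | 2.8016/1 − 1.96 = 0.842 | 80.0% |
| 0.05 | 5.3% | 2.8016/0.9747 − 1.96 = 0.914 | 82.0% |
| 0.10 | 11.1% | 2.8016/0.9487 − 1.96 = 0.993 | 84.0% |
| 0.20 | 25.0% | 2.8016/0.8944 − 1.96 = 1.172 | 87.9% |

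As a concrete case, assume a standardised difference of 0.5 and 1:1 allocation. The unadjusted test then needs 63 lesions per arm (power 80.1%). With R² of 0.05, 0.10 and 0.20 the requirement falls to 60, 57 and 51 per arm.

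**Step 2: cost of one continuous covariate.** With N lesions in total, the ratio of adjusted to unadjusted variance is about (1 − R²)(1 + 1/(N − 4)). Adjustment breaks even at R² = 1/(N − 3).

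| N | Ratio at R² = 0 | Ratio at 0.05 | Ratio at 0.10 | Ratio at 0.20 | Break-even R² |
|---|---|---|---|---|---|
| 30 | 1.038 | 0.987 | 0.935 | 0.831 | 3.7% |
| 60 | 1.018 | 0.967 | 0.916 | 0.814 | 1.8% |
| 100 | 1.010 | 0.960 | 0.909 | 0.808 | 1.0% |
| 200 | 1.005 | 0.955 | 0.905 | 0.804 | 0.5% |

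If size explains nothing, 80% power becomes Φ(2.8016/√1.010 − 1.96), about 79.6%, at 100 lesions. At 30 lesions it becomes Φ(2.8016/√1.038 − 1.96), about 78.5%.

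**Step 3: why mm rather than bands.** Entering size as three bands uses two degrees of freedom. The ratio is then about (1 − R²)(1 + 2/(N − 5)), with break-even R² of 7.4% at 30 lesions and 2.1% at 100, about twice the figures above.

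**Step 4: validity.** A simulation with 4,000 replicates per setting compared the t-test with the three-band model at N = 40 and N = 128. It assumed band shares of 15%, 60% and 25% and R² from 0 to 0.20. Type I error was 4.8% to 5.5% for the t-test and 4.4% to 5.6% for the adjusted model. Under no treatment effect, the variance ratio ran from 1.062 (R² = 0) to 0.854 (R² = 0.20) at N = 40, and from 1.016 to 0.808 at N = 128. With respect to size, both analyses are valid and differ only in precision.

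**The case against.** The strongest case against is that nothing here is wrong and the benefit is unproven. Much of that stands.

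- **The plan does not predict a size effect.** A reader might infer that the plan expects size to influence pain. The wording "To see if lesions size had any effect on these metrics" is an open question, asked of pain, reinjection and bleeding together, and no evidence is cited. The documents support only a possible influence.
- **There is no bias.** A reader might infer that a chance size imbalance invalidates the t-tests. Under randomisation it does not: the test's error rate already covers chance imbalance, and the simulation agrees.
- **The gain is unknown.** A reader might infer that the intervals are certainly too wide. That holds only if size predicts pain. The bands are analysis cut-points and do not show how sizes are distributed; if most lesions fall in one band, size may explain little. Nothing in the documents suggests that size predicts injection pain in particular. For procedure pain, the reinjection and switching steps in the Study Protocol could absorb part of any size effect before the score is taken.
- **It is not free.** Sorting lesions into three bands needs less accuracy than a value in mm, and no measurement step is described.
- **Arm plus size is not a complete model.** It would still treat lesions from one patient as independent, as the t-test does. That is a separate issue, and the documents give no within-patient correlation with which to size it, but the same model can deal with it.

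These objections limit the claim without removing it. The banded analysis already requires a size for every lesion, the loss if size is irrelevant is small and bounded, and the gain at moderate R² is useful.

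**Conclusion.** The point holds as a modest matter of efficiency. The plan uses a characteristic that it needs for every lesion only in repeats that cannot sharpen the primary result. Under assumed R² of 0, 0.05, 0.10 and 0.20, 80% unadjusted power becomes about 80% (very slightly less), 82%, 84% and 88%. In the worst case, where size explains nothing, variance rises by about 4% at 30 lesions and 1% at 100.

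These figures rest on an assumed R², a linear effect of size, independent lesions and two-sided alpha 0.05; none of these comes from the documents. They describe lesion size alone. A reader might expect more from also adjusting for a pain score taken before injection, but the Study Protocol collects none, so no such gain is counted here.

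**What to change.** In the Statistical Plan, replace the two primary t-tests with a linear model for each pain score, containing arm and lesion size in mm. State in advance whether size enters as mm or log mm. Report the adjusted arm difference with its 95% CI as the primary result, with the unadjusted difference alongside. Allow for several lesions in one patient, for example with a random patient effect. Declare all this before outcome data are seen, so that the choice between adjusted and unadjusted results cannot follow the data. The size bands can stay as a secondary description.

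In the Study Protocol, add that lesion size in mm is recorded before allocation, for example from the photograph already taken at that stage if it allows measurement.

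The cost is a few sentences, about one degree of freedom for size, and one measurement in mm per lesion. No extra patients are needed.

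### Four arm comparisons repeated in three lesion-size groups, with no stated error control, make a chance size-group finding fairly likely

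*Combined protocol and SAP*

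**What the plan says.** The Statistical Plan sets out two t-tests: "Pain of injection and pain of procedure are recorded on a categorical scale and compared using Student T-Tests". It adds two chi-square tests, one on the share of lesions reinjected and one on the share with severe bleeding ("bleeding were compared using Chi-square tests").

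Its last sentence turns to lesion size. The aim is "To see if lesions size had any effect on these metrics"; the method is that "the lesions will be divided into < 1 mm, 1-5 mm, and > 5 mm" and the "analysis will be repeated on these groups".

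The documents give no significance level, sidedness, multiplicity adjustment, sample size or interaction analysis. They do not say that the size-group results are exploratory, and they do not limit what may be concluded from them.

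**The concern.** Followed as written, the plan answers the size question by seeing which groups reach significance. This causes two problems.

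- Twelve further tests give chance many openings. One small p-value could be reported as showing that saline is better, adequate or worse for bleeding in lesions of one size. Because the Clinical question asks whether saline anesthetizes adequately in minor eyelid procedures, a conclusion by lesion size would be a natural one to draw.
- Significance in one group and not in another does not show that the groups differ. The same true arm difference can cross the threshold in a large group and miss it in a small one.

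Adding an interaction analysis while keeping the 12 within-group tests would solve the second problem but not the first.

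**Working it through.** The plan states no error rate, so there is no figure of its own to reproduce.

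**Inputs from the Statistical Plan.** Tests per analysis: 2 t-tests + 2 chi-square tests = 4. Size groups: 3. Size-group tests: 4 × 3 = 12.

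**Assumed, because the documents are silent.** Two-sided 0.05 per test; group sizes, event rates and correlation between metrics as shown below.

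**1. Independent tests.** The chance of at least one false positive among k null tests is 1 − (1 − α)^k.

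- All 12 null, α = 0.05: 1 − 0.95^12 = 46.0%
- Same at α = 0.01: 1 − 0.99^12 = 11.4%
- Same at α = 0.10: 1 − 0.90^12 = 71.8%
- Injection pain truly differs, other three metrics null (9 tests): 1 − 0.95^9 = 37.0%
- Two metrics truly differ (6 null tests): 1 − 0.95^6 = 26.5%

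The six size-group pain tests alone also give 1 − 0.95^6 = 26.5%, so the problem does not depend on how the chi-square tests behave when events are sparse.

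**2. Correlated metrics.** Different size groups hold different lesions, so correlation is placed between the four metrics within a group. Simulating three independent groups of four equally correlated test statistics (400,000 runs, α = 0.05) gives:

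| Correlation | At least one significant |
|---|---|
| 0.3 | 43.7% |
| 0.5 | 39.8% |
| 0.6 | 37.4% |
| 0.7 | 34.2% |
| 0.8 | 30.5% |
| 0.9 | 25.5% |
| 1.0 | 14.3% |

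The last row agrees with three effective tests: 1 − 0.95^3 = 14.3%.

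**3. The planned tests themselves.** Simulated with no arm effect: t-tests on scores rounded to 0–10 (underlying mean 3, SD 2) and chi-square tests with and without the Yates correction, because the plan does not say which. Lesions per arm in the three groups were 5/15/10, 3/25/12, 20/20/20 or 50/50/50; correlation was 0, 0.3 or 0.6; 6,000 runs per setting.

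| Reinjection / severe bleeding | Uncorrected | Yates |
|---|---|---|
| 20% / 20% | 35.8–47.3% | 26.5–37.8% |
| 20% / 5% | 31.4–44.9% | 25.6–33.5% |
| 10% / 3% | 28.1–42.1% | 25.1–32.2% |

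The overall range is about 25–47%. The low end occurs when the chi-square tests rarely reject and the pain tests supply nearly all the false positives.

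**4. Reading the groups against each other.** For one metric with no arm difference in any group, the chance that the three groups disagree on significance is 1 − 0.95^3 − 0.05^3 = 14.25%. Over four independent metrics, the chance that at least one shows such a split is 1 − (1 − 0.1425)^4 = 45.9%. Nearly every false positive would therefore also look like an effect of lesion size.

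**Not sized.** "Each lesion will be randomized separately", so one patient may supply lesions to several groups or to both arms, which the planned tests ignore. This could move the figures either way, and the documents give nothing from which to estimate it.

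**The case against.** The strongest reply is that this is a routine subgroup look that few readers would treat as confirmatory. Lesion size is absent from the Clinical question and from Outcome Measures; it appears only in the last sentence of the Statistical Plan. Outcome Measures also ranks the outcomes: pain is primary, while bleeding and further anesthesia are secondary. This much stands. A reader might infer that the size-group tests have equal standing with the overall ones, or that the plan has a rule allowing a claim from a single group. The text supports neither; it simply leaves the standing of these results unstated.

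Two other strong readings also fail:

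- A reader might infer that the plan tests each group at a full 5%. No level is stated, so 0.05 is an assumption, and the figure moves from 11.4% to 71.8% as the level goes from 0.01 to 0.10.
- A reader might infer that a false size-group finding is about as likely as not. That describes only the top of the range, and only if no metric differs between arms. The Introduction leads one to expect less injection pain with saline. Reinjection is also triggered by pain during the procedure, so at least those two metrics may be strongly linked.

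It can also be said that a 95% confidence interval excluding no difference is nearly the same thing as p < 0.05, so replacing tests with intervals changes little. This is correct for intervals alone. It is why the fix must bar claims based on where an interval falls, and must give the size question an analysis of its own.

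None of this removes the defect. The stated purpose is to learn whether size has an effect, the stated method is to repeat the tests, and nothing commits the sponsor to treating the results as exploratory.

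**Conclusion.** The point holds as a weakness in the stated method. Twelve size-group tests without error control are to be used to judge whether lesion size matters, which they cannot do directly.

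At an assumed two-sided 0.05 and with no arm difference on any metric, the chance of at least one nominally significant group result is 46% under independence and roughly 25–47% over the settings examined. Even 25% is five times the nominal rate of a single test. The lower figure is not an absolute floor, since perfectly correlated metrics would give 14.3%. If injection pain alone truly differs, the figure is 37% under independence.

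The overall arm comparisons are not affected by this point. What is exposed is any conclusion about lesions of a particular size. The change is worth making because it is cheap.

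**What to change.** In the Statistical Plan, replace "analysis will be repeated on these groups" with:

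> within each size group the arm difference in each metric is reported descriptively as an estimate with a 95% confidence interval, without a significance test, and no claim of benefit, adequacy or harm is based on a single size group, including on whether its interval excludes no difference; whether the arm difference varies with lesion size is assessed by one arm-by-size interaction estimate per metric, labelled exploratory.

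One estimate per metric implies entering the three groups as an ordered score; unordered groups would need two contrasts per metric. The SAP should say which is meant. The exploratory label matters here too: if the four interactions were instead tested at 0.05 each, the chance of at least one false positive under independence would be 1 − 0.95^4 = 18.5%.

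If the sponsor prefers to keep the within-group tests, a Bonferroni level of 0.05/12 = 0.00417 would hold the error over the 12 tests to 1 − (1 − 0.00417)^12 = 4.9% under independence. That would still leave the size question without a direct comparison.

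The cost is one sentence of SAP wording and no new data. The sponsor gives up calling a single size-group result significant, and the interaction estimates will be imprecise, particularly for severe bleeding if it is rare. The change does not address multiplicity among the four overall comparisons or several lesions from one patient.
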